1.3 Secondary Objectives

Secondary objectives include: in our study sample,

- (1) Test the efficacy of the mini-app in decreasing PrEP stigma and increasing PrEP use self-efficacy at the individual level.
- (2) Identify the predictors associated with successful PrEP initiation during the study period.
- (3) Investigate the association between depression at baseline and successful PrEP initiation during the study period.
- (4) Assess PrEP use adherence among participants who successfully started PrEP during the study period.

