2.0 INTRODUCTION

2.1 Background

The prevalence of HIV among Chinese men who have sex with men (MSM) has steadily increased for the past decade. According to the National HIV Sentinel Surveillance System, the prevalence of HIV in Chinese MSM rose from 1.5% in 2005 to 8.0% in 2015.¹ Overall, MSM comprise over a quarter of new HIV diagnoses in China, this greater than three times the rate in other countries.² These trends continue to rise as China works to implement feasible and sustainable HIV prevention measures.

Pre-exposure prophylaxis (PrEP) is a once daily oral fixed-dosed combination of two antiretroviral medications, tenofovir disoproxil fumarate (TDF) and emtricitabine (FTC) also referred to as TDF/FTC. Several clinical trials have demonstrated that PrEP is safe and significantly reduces the rate of HIV acquisition in MSM,³ heterosexual HIV sero-discordant couples,⁴ heterosexual individuals,⁵ and persons who inject drugs.⁶ Based on these studies, in

2014, the United States Centers of Disease Control and Prevention (CDC) issued recommendations for PrEP in MSM, high risk heterosexual men and women, and PWID. These recommendations were updated in 2017 with more trials further supporting PrEP use in these key populations.⁷ In 2014, the World Health Organization (WHO) recommended global access to PrEP for MSM which was then expanded in 2015 to include all populations at substantial risk of HIV infection.⁸

Despite the current HIV landscape of China and the proven safety and efficacy of PrEP, uptake remains limited with only an estimated 400-600 current PrEP users in the country.⁹ The delay in PrEP expansion in China is likely multifactorial, including limited awareness of PrEP, HIV and sexuality-related stigma and discrimination, concerns of PrEP effectiveness and side effects, and financial concerns to afford PrEP.¹⁰⁻¹³ Initial PrEP demonstration projects in China were unsuccessful because of poor community engagement and lack of community ownership.¹¹ Bottom-up approaches such as challenge contests provide a tool for MSM to be more actively engaged in HIV service delivery.¹⁴ A recent multisite survey of urban Chinese MSM showed while nearly half of the respondents endorsed unprotected anal sex, less than a quarter had heard of PrEP.¹⁵ These studies indicate a need in using an MSM-friendly approach to promote PrEP uptake among this at-high-risk population and linking them to PrEP to help stem the ongoing epidemic.

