Participants in both arms can choose to initiate PrEP at any time point since the initial visit until the end of 8th week. Participants can contact the study team via phone call, text messages or via the chat function in the mini-app to communicate their interest in PrEP initiation. If baseline assessment or follow-up survey results do not show contradictions to PrEP initiation, interested participants will be referred to the Department of Infectious Diseases at Guangzhou No.8 People's Hospital to consult a clinician regarding HIV risks and PrEP eligibility. As is standard of care for any patient starting PrEP, participants will take comprehensive physical examinations (including routine urine examinations, hepatic and renal function tests, blood glucose and lipids, and bone mineral density (BMD)). The study team will not have access to participants' medical records (i.e. the physical examination results). Participants who are confirmed by the clinician HIV-negative, with no serious liver or kidney dysfunction and negative for HBs antigen, without serology indicating osteoporosis, without clinical signs or symptoms consistent with acute viral

infection, will be prescribed either 8-week daily oral TDF/FTC or event-driven oral TDF/FTC based on participants' preference. The cost of physical examinations in order to get PrEP prescription will be covered by the study team. If a participant is eligible for starting PrEP and have been prescribed PrEP by a PrEP provider, the participant will get a 50% reimbursement of the cost for their first two months of PrEP doses (30 pills/month, up to 60 pills in total) filled at the in-house pharmacy of the study hospital (the Guangzhou Eighth People's Hospital).

Follow-up and Data collection

The active intervention period will last for 8 weeks, but participants in the intervention arm can have access to the mini-app throughout the whole study period or until the end of their first two-month PrEP use, which can be as long as 16 weeks. Baseline assessments will be conducted at the enrollment visit, with follow-up assessments conducted at 2, 4, 6, 8, 12 (post-intervention). Participants from both arms will need to complete a self-administrated Web-based survey at each assessment time point.

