4.3 Study Enrollment Procedures

Participant recruitment will be targeted to venues (health clinics, gay bar) and mediums (e.g. Internet, social media) that we have identified from past formative work to be frequented by MSM in Guangzhou, and specifically MSM who are seeking HIV testing or post-exposure prophylaxis.

Aim 1: Potential participants will be verbally screened for eligibility during their initial contact with the study team, before proceeding to the full informed consent and enrollment in in-depth interviews. All enrolled participants will be given a unique ID number for identification purposes.

Aim 2: Potential participants will be verbally screened for eligibility during their initial contact with the study team, before proceeding to the full informed consent and enrollment in the RCT. All enrolled participants will be given a unique ID number for identification purposes.

We will conduct a simple randomization that randomly assign the 70 participants to either the mini-app arm (n=40) or the control arm (n=30). Based on the timing of enrolling the study, each participant will be assigned a two-digit study ID (e.g., the first enrolled participant will be ID01; the second will be ID02; the last one enrolled will be ID70). Before enrollment, the study team will use the Microsoft Excel program to randomly assign the 70 IDs into group A (the intervention arm) and group B (the control arm). Once enrolled, a participant will be automatically assigned to either the intervention arm or the control arm based on his ID. If a participant quitted the study because of non-PrEP-related reasons (e.g., seroconversion, moving to other cities) after enrollment, we will recruit a new participant for replacement.

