6.3 Quantitative Outcome Measures

Quantitative outcome measures will be assessed in Aim 2 through baseline and follow-up assessments.

Primary Outcome Measures: The primary outcome is PrEP initiation, measured by the number of participants who successfully initiated PrEP during the 8-week intervention period.

Secondary Outcome Measures: Secondary outcomes include self-report PrEP use self-efficacy, PrEP stigma, PrEP adherence (among those who are on PrEP), sexual risk behaviors, sexually transmitted infection incidence, general stress and HIV-related stress.

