8.6 Analyses

Descriptive statistical analysis will be first conducted to report demographic characteristics of participants, PrEP uptake rates, PrEP-related perceptions, PrEP adherence, HIV/STI testing behaviors, prevalence of STIs, mini-app use behaviors at different time points throughout the study period. Statistical tests including Chi-Square tests and t-tests will be conducted to compare the preliminary intervention effects (i.e. the efficacy of mini-app in improving PrEP-related perceptions, increasing PrEP uptake rates and HIV/STI testing behaviors) between the intervention group and control group at each time point. Multivariate logistic regression models will be applied to estimate the association between intervention arm and the primary study outcome, PrEP initiation during the 8-week intervention period. If prognostic factors associated with the primary outcome remain insufficiently balanced through simple randomization, we may adjust for these factors in our models. Potential confounding factors that may be included are perceived HIV infection risk, PrEP self-efficacy and perceived PrEP stigma.

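### Section 8.6 gives the primary effect to logistic regression in 40 v 30 men with no sparse-data rule; if control uptake is about 5% or lower, the odds ratio may well not exist.

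*Combined protocol and SAP*

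**What the plan says.** The primary outcome in section 6.3 is PrEP initiation, "measured by the number of participants who successfully initiated PrEP during the 8-week intervention period". Sections 4.3 and 8.3 randomise 70 men, 40 to the app and 30 to control.

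For the analysis, section 8.6 states: "Multivariate logistic regression models will be applied to estimate the association between intervention arm and the primary study outcome". Adjustment is optional: "Potential confounding factors that may be included are perceived HIV infection risk, PrEP self-efficacy and perceived PrEP stigma". The same section plans simple between-arm tests at each time point, PrEP uptake included: "Statistical tests including Chi-Square tests and t-tests will be conducted to compare the preliminary intervention effects". It also plans descriptive uptake rates.

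Section 8.6 does not say whether the logistic model is fitted by ordinary, penalised or exact methods, whether inference is Wald or likelihood-ratio, what happens if one arm has no initiators, or whether the chi-square or the logistic result governs. No section gives an expected initiation rate, an alpha or a power. Section 8.4 says that the control arm is there to yield an effect size for powering a later full-scale trial.

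**The concern.** Logistic regression by ordinary maximum likelihood has no finite solution for the arm effect when one arm has no events. With 30 controls this can plausibly happen if few of them start PrEP, and section 2.1 describes national uptake as low: "uptake remains limited with only an estimated 400-600 current PrEP users in the country".

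A result of many initiators on the app and none in control would favour the app most, yet the only model named for the primary outcome would then return no usable odds ratio. If software reports its usual Wald p-value, that p-value is close to 1. The planned chi-square could be clearly significant on the same data. The report would carry two conflicting p-values with no rule between them, and no odds ratio to hand to the next trial, which is what section 8.4 wants from this pilot.

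**Working it through.** The plan states no rate, power or event count, so there is no figure of its own to reproduce.

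**Inputs from the protocol.** n = 40 and 30 (4.3, 8.3); binary outcome at 8 weeks (6.3); logistic model and chi-square test (8.6).

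**Assumptions.** Two-sided alpha 0.05. Control uptake 2% to 20%, app uptake 20% to 50%. Wald inference, a common software default that 8.6 does not specify. No dropout. A non-estimable Wald result counts as non-significant.

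**1. Chance of no control initiators.** P(0 of 30) = (1 − p)^30.

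| Control uptake p | P(0 of 30) |
|---|---|
| 2% | 0.98^30 = 0.55 |
| 5% | 0.95^30 = 0.21 |
| 10% | 0.90^30 = 0.04 |
| 15% | 0.85^30 = 0.008 |
| 20% | 0.80^30 = 0.001 |

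**2. What the methods give for 8/40 v 0/30.**
- Odds ratio: (8 × 30)/(32 × 0), infinite. A software fit stops at a log odds ratio of about 22 with standard error about 14,500, so Wald p = 0.999. Even 16/40 v 0/30 gives Wald p = 0.999.
- Pearson: 70 × (8 × 30 − 32 × 0)² / (40 × 30 × 8 × 62) = 6.77, p = 0.009.
- Likelihood ratio: 2 × [−20.02 − (−24.88)] = 9.72, p = 0.002.
- Firth: (8.5 × 30.5)/(32.5 × 0.5) = 15.95, penalised-likelihood p = 0.007, 95% interval 1.85 to about 2096.
- Risk difference: 20 points. The Wilson limits are 10.5% to 34.8% for 8/40 and 0% to 11.4% for 0/30. The Newcombe limits are therefore 20 − √(9.5² + 11.4²) = 5 points and 20 + √(14.8² + 0²) = 35 points.

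**3. One control initiator.** For 8/40 v 1/30 the log odds ratio is ln(8 × 29/32) = 1.981. Its standard error is √(1/8 + 1/32 + 1/1 + 1/29) = 1.091, so Wald p = 0.069. Pearson gives 0.039 and the likelihood ratio 0.027. For 10/40 v 1/30, Wald p = 0.036.

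**4. Exact power** (all 41 × 31 possible tables, binomial weights).

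| Control v app uptake | Pearson | Wald | Likelihood ratio |
|---|---|---|---|
| 2% v 20% | 72% | 15% | 80% |
| 5% v 20% | 47% | 19% | 53% |
| 5% v 30% | 83% | 55% | 84% |
| 10% v 30% | 56% | 45% | 56% |
| 20% v 50% | 77% | 74% | 77% |

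**5. Where the gap comes from.** At 5% v 20%, Pearson is significant and Wald is not in 28% of trials; 20 of those 28 points are tables with no control initiator. At 10% v 30% the zero cell gives 4 of 11 points. Among trials with 1 to 3 control initiators, Wald loses about 9 to 14 points of power at control uptake of 2% to 10%. In counts, the app arm needs one more initiator for significance under Wald than under Pearson: 9 v 8, 11 v 10 and 13 v 12 for 1, 2 and 3 control initiators.

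**6. Size** (maximum over a common uptake of 1% to 50%). Pearson 5.3%, Wald 4.9%, likelihood ratio 7.4%, Firth penalised likelihood ratio 5.1%. Firth power is 47.1% at 5% v 20%, 82.8% at 5% v 30% and 55.9% at 10% v 30%, in line with Pearson.

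**The case against.** **Low control uptake is not in the documents.** A reader might infer from section 2.1 that few initiators are expected. That figure is a national count of users, not a forecast for this sample. The trial enrols men with a recent HIV risk criterion (4.1) and targets men seeking testing or post-exposure prophylaxis (4.3). In both arms it pays for the examinations, and "the participant will get a 50% reimbursement of the cost for their first two months of PrEP doses" (3.0). Uptake could be well above 10%, and at 15% to 20% the power gap is only 3 to 4 points. This stands, and makes the point conditional. It does not remove it, because the plan states no rate that would rule the problem out.

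**Wald inference is not specified.** This also stands. A likelihood-ratio test of the same model is significant where Wald is not. It is only a partial escape: its size reaches 7.4% at these sample sizes, and the odds ratio stays infinite.

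**The trial would not be left without a test.** A reader might infer that a zero cell leaves no usable result. It does not: 8.6 already plans the chi-square and the uptake rates, so 20% v 0% with p = 0.009 would be reported. What is missing is an interval for the effect and a statement of which result governs.

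**Two other strong readings go too far.** One is that the Wald test is nearly useless with 1 to 3 control initiators; the loss there is moderate. The other is that the fitted odds ratio, when finite, is inflated by a known factor. That factor depends on covariate effects the documents do not give, and adjustment is optional.

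**Conclusion.** The point holds conditionally. As written, 8.6 relies for its only modelled estimate of the primary effect on a method that fails when no control initiates, and it sets no rule for that case. At control uptake of 5% or lower the chance of this is 21% or more, and Wald power falls well below Pearson power (19% v 47% at 5% v 20%). At 10% the chance is 4% and the power gap is 11 points; at 20% the issue nearly disappears.

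The size rests on two assumptions that the documents neither confirm nor exclude: low control uptake, and Wald inference. The infinite odds ratio depends only on the first, given ordinary maximum likelihood. The documents do not support saying that the trial expects few initiators or that it would have no valid test. It is a should-fix point at the level of wording, worth making because section 8.4 wants an effect size from this pilot.

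**What to change.** In section 8.6:

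- Make the primary estimate the week-8 difference in the proportion initiating PrEP (app minus control), with a Newcombe or Miettinen-Nurminen 95% interval, tested by the Pearson chi-square already planned. State that this result governs.
- Fit any adjusted model by Firth penalised logistic regression, with a penalised-likelihood interval and p-value, and label it supportive.
- Name the risk difference as the effect size to carry into the next trial.

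The cost is SAP wording and a standard software option; no new data are needed. The limitation is that Firth makes the odds ratio finite but not precise: with a zero cell the upper limit stays very wide (about 2096 for 8/40 v 0/30), which is why the risk difference should lead.

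Objective 1.3(2), "Identify the predictors associated with successful PrEP initiation during the study period", draws on the same few events, and Firth estimation suits it too. I do not propose limiting that model to arm plus the three factors named in 8.6. That would be a trade-off, and it would leave out baseline depression, which objective 1.3(3) needs.

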7.0 PARTICIPANT WITHDRAW AND REPORT

Participants may voluntarily withdraw from the study for any reason at any time. No further data collection will occur from the date the decision is made to permanently discontinue the participant from the study. The study investigators also may withdraw participants from the study in order to protect participant or staff safety. Study staff will record the reasons for all withdrawals.

If a participant fails or is unable to comply with study procedures they will be withdrawn from the study. Participants will be withdrawn if they:

- are noticeably intoxicated or on illegal drugs.
- threaten a study staff member.
- are mentally handicapped and unable to give full informed consent.
- are incarcerated during course of study.
- become HIV-positive during course of study.
- reporting severe medication side effects after initiating PrEP and are advised to quit the study by a HIV specialist.

Any enrolled participant who report any of the above-mentioned events will be immediately stop participation in the study, and study staff will complete a Study Stop form for participants who are discontinued. This form will include the date, last research activity completed, and reason for study discontinuation. These will be reported to the UNC IRB and the Guangzhou No.8 People's Hospital IRB at the end of study.

Reporting is required of all unanticipated problems to the UNC IRB, including those which may occur after the participant has completed or has withdrawn from the study, including after study closure.

Unanticipated problems as defined by the UNC IRB:

Unanticipated problems involving risks to participants or others" or "Unanticipated Problem" refers to any incident, experience, or outcome that:

- is unexpected (in terms of nature, severity, or frequency) given (a) the research procedures that are described in the protocol-related documents, such as the IRB-approved research protocol and informed consent document; and (b) the characteristics of the participant population being studied;
- is related or possibly related to a participant's participation in the research; and
- suggests that the research places participants or others at a greater risk of harm (including physical, psychological, economic, or social harm) related to the research than was previously known or recognized.

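### Randomised leavers are replaced (4.3) and their data collection stops (7.0), but no section says whether they, or participants with unknown week-8 status, count in the PrEP-initiation analysis

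*Combined protocol and SAP*

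**What the plan says.** **Replacement and IDs (4.3).** Before enrolment, "the study team will use the Microsoft Excel program to randomly assign the 70 IDs into group A" and group B, and each participant takes the arm attached to his ID on enrolment. The last person enrolled is to be ID70. For someone who quits "because of non-PrEP-related reasons (e.g., seroconversion, moving to other cities) after enrollment, we will recruit a new participant for replacement". Nothing states which ID or arm the newcomer receives.

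**Withdrawal (7.0).** "If a participant fails or is unable to comply with study procedures they will be withdrawn from the study". The same list covers participants who become HIV-positive and those advised to leave after severe side effects once on PrEP. On data: "No further data collection will occur from the date the decision is made to permanently discontinue the participant from the study".

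**Outcome (6.3).** PrEP initiation is a count of participants over the 8-week intervention period, taken from the study's baseline and follow-up assessments. No denominator is given.

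**Analysis (8.6).** Logistic regression is assigned to the primary outcome. On covariates: "If prognostic factors associated with the primary outcome remain insufficiently balanced through simple randomization, we may adjust for these factors in our models". Then: "Potential confounding factors that may be included are perceived HIV infection risk, PrEP self-efficacy and perceived PrEP stigma". Chi-square and t-tests compare outcomes "between the intervention group and control group at each time point". Neither 8.6 nor any other section defines an analysis set or a rule for missing outcome data.

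**Use of the result (8.4).** The study is called a pilot of preliminary efficacy. The control arm is said to permit estimation of an effect size good enough to power the full trial.

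**The concern.** Arm is assigned on enrolment, so anyone who leaves after enrolment has already been randomised. If the trial is filled to 40 and 30 by swapping leavers for newcomers, the natural reading of those totals leaves the departed participants out. That would do little harm if leaving were unrelated to PrEP initiation, but the documents tie the two together in several places. The comparison would then no longer be between the groups that randomisation created.

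A missed week-8 survey raises the same question in a milder form: without a rule, the team decides after seeing the data whether such a person is a non-initiator or is dropped. The optional adjustment in 8.6 adds a smaller choice of the same kind. Efficacy for uptake is a primary objective (1.2), and 8.4 carries the estimate into the next trial's planning.

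**Working it through.** **Plan's own figure.** 40 + 30 = 70 agrees with 4.3 and 8.3. Section 8.4 contains no calculation and gives no error level, power, uptake rate or expected loss. Every rate below is therefore an assumption.

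**Is leaving linked to the outcome?**
- Seroconversion: 4.3 classes it as unrelated to PrEP and replaces the participant; 7.0 withdraws him. Section 3.0 (PrEP initiation) requires confirmed HIV-negative status for a prescription, so he cannot initiate afterwards.
- Severe side effects: 7.0 withdraws people who have already started PrEP. All are initiators, and on its face their reason falls outside the replacement rule.
- Non-compliance: 7.0 withdraws them; 4.3 does not say whether this leads to replacement.
- IDs: the list ends at 70. A newcomer must either take over a leaver's ID or come from an extended list, and neither is stated.

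**If leavers are dropped and there is no true effect.** Let p be true uptake, a the fraction of initiators dropped and d the fraction of non-initiators dropped. Expected observed uptake is p(1-a) / [p(1-a) + (1-p)(1-d)]. Take p = 0.20 in both arms.
- Control, a = 0, d = 0.10: 0.20/(0.20 + 0.72) = 21.7%.
- App, a = 0, d = 0.30: 0.20/(0.20 + 0.56) = 26.3%; difference +4.6 points.
- App, a = 0.10, d = 0.30: 0.18/(0.18 + 0.56) = 24.3%; difference +2.6.
- App, a = 0.10, d = 0.10: 0.18/(0.18 + 0.72) = 20.0%; difference -1.7.
- Equal losses in both arms (a = 0, d = 0.10): difference 0.

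**Unknown status, with 10/40 against 3/30 observed initiators.**
- Unknown counted as not initiated: 25.0% - 10.0% = 15.0 points.
- 10% unknown (4 and 3), dropped: 10/36 - 3/27 = 16.7.
- 10% unknown, extremes: 10/40 - 6/30 = 5.0, and 14/40 - 3/30 = 25.0.
- 20% unknown (8 and 6), dropped: 10/32 - 3/24 = 18.8; extremes 10/40 - 9/30 = -5.0 and 18/40 - 3/30 = 35.0.
- If 4 and 3 leavers, none an initiator, were replaced and are kept in: 10/44 - 3/33 = 13.6.

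**Adjustment.** The standardised difference for one factor has SE = sqrt(1/40 + 1/30) = 0.24. Chance alone exceeds 0.10, 0.20 or 0.25 in 68%, 41% or 30% of trials. For at least one of three independent factors, 1 - (1-q)^3 gives 97%, 79% or 66%. These are upper limits, because 8.6 also requires an association with the outcome.

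Simulated false-positive rates at a nominal 5%, with three independent factors, 20% or 30% uptake and log-odds of 0 to 0.8 per SD:
- unadjusted: 3.8-5.0%;
- a trigger at 0.25 followed mechanically: 3.8-4.6%;
- the most favourable of all eight covariate subsets: 5.4-10.0%.

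A separate simulation at 20% uptake, with an assumed trigger, took only the better of the adjusted and unadjusted results. It gave at most 7.3%, against 5.4% unadjusted.

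**Section 8.4.** For 10/40 against 3/30, the Newcombe 95% interval is -4.0 to +31.5 points.

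**The case against.** This is a pilot, and much of the unknown status may be recoverable. Surveys run at weeks 2, 4, 6, 8 and 12. The study pays for the pre-prescription examinations and reimburses part of the drug cost. Section 7.0 stops only further data collection, so a side-effect leaver's initiation may already be on record. That stands, and it makes the 20% bounds an outer limit. But no section commits to using these sources, and the team cannot see medical records (3.0).

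A reader might infer more than the documents support:
- *Replacement favours the app.* The loss patterns are assumed, and plausible changes reverse the sign.
- *The plan excludes leavers.* It does not say so; it is silent.
- *The imbalance trigger inflates false positives.* Followed mechanically it does not; the room lies in the optional wording.
- *Covariates might be measured after baseline.* Two of them are also outcomes ("Secondary outcomes include self-report PrEP use self-efficacy, PrEP stigma, PrEP adherence"), but balance achieved by randomisation makes sense only for baseline values. Adding the word baseline is a clarification.
- *Tests at several visits undermine the primary result.* 8.6 gives the logistic model to the primary outcome over a fixed 8-week window, so p-values at other visits need not be removed.
- *8.4 will size the next trial on the point estimate alone.* It does not say that, and it describes a different trial, with 12-month follow-up and multilevel models.

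**Conclusion.** The main point holds. As written, the plan allows randomised participants to disappear from a 40/30 analysis for reasons connected with PrEP initiation, and leaves unknown week-8 status to be settled later. This rests on the text, not on any assumed rate. The illustrations show only that the effect could be a few points in either direction, and that 10% unknown status is compatible with anything from 5 to 25 points when the nominal difference is 15.

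The adjustment point is minor. Three candidate factors are named, and the cost of leaving the choice open is modest: about two percentage points of extra false positives when the choice is between two results. It reaches 10% only with strong factors and a free search over every subset. Section 8.4 is a separate wording matter: the interval at 40 against 30 is too wide for the claim made. All of this should be corrected before outcomes are seen. None of it invalidates the pilot.

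**What to change.** **8.6, main change.** Analyse everyone randomised in the assigned arm, including leavers who are replaced. Count a participant as having initiated if any survey, or the study's own reimbursement record, shows a start by week 8 (or before withdrawal); otherwise count him as not initiated. Apply the same rule to withdrawal and to missed surveys, and show the two extreme bounds.

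**4.3.** State that each replacement receives a new ID with its own random arm from an extended list, prepared before the first replacement, and neither takes over nor removes the leaver's ID.

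**8.6, minor.** Delete the imbalance trigger. Name one primary estimate now: the unadjusted arm effect with a 95% CI, either as a risk difference or from the logistic model already planned. Add one sensitivity model, fitted whatever the balance, with baseline perceived HIV risk, PrEP self-efficacy and PrEP stigma.

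**8.4.** Say that the pilot will give control-arm uptake and an interval for the difference.

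**Cost.** Wording and a longer ID list; no new data collection and no change to the withdrawal rules. Arm sizes may differ from 40/30. Counting unknowns as not initiated may slightly understate uptake, and reimbursement records cover only fills at the study hospital; hence the bounds. The sensitivity model is weak: about 13 events for four coefficients (13/4 = 3.25 each), which is why it should not be primary. The team gives up some freedom to adjust afterwards.
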